2.3 Imputation Algorithm

[figure not shown]
It is reasonable to assume the missing values of the longitudinal data for an outcome variable (e.g., abscess count at each post-baseline visit) follows a monotone missing pattern. In practice, the missing data of the outcome variable might have an arbitrary (non-monotone) missing data pattern. An extra step may be added accordingly, to augment data into a monotone missing pattern.

For the outcome variable (e.g., abscess count at each visit), K 'complete' datasets can be generated in two steps: augmentation step and imputation step. K, the number of repetitions, is determined below.

Augmentation Step

For datasets with non-monotone missing data pattern, the augmentation step will first impute enough values to augment the data into a monotonic missing pattern:

Markov Chain Monte Carlo (MCMC) will be applied to augment the data using PROC MI with the MCMC IMPUTE=monotone statement, assuming a multivariate normal distribution. The augmented data will be used in the subsequent imputation step to generate 'complete' datasets. Covariates included in the model are treatment group, prior exposure to anti-TNF category, Baseline worst Hurley Stage, Baseline abscess count, all

post-baseline visits of abscess count up to the end of the Study Period. Of note, categorical variables are included using the form of dummy variables.

Repeat the imputation process K=30 times using the procedure described above to form K=30 monotone missing datasets, where K is determined as described in "Repetition of Imputations (K)."

Imputation Step

For missing data with monotone missing patterns, the choice of multiple imputation using a parametric regression model that assumes multivariate normality is appropriate.

The imputation step is described below:

- The imputation model for the missing data is a regression model, which controls for treatment group, prior exposure to anti-TNF category, Baseline worst Hurley Stage, Baseline abscess count, all post-baseline visits of abscess count up to the end of the Study Period. The covariates included in the model and the order of these variables are consistent with the augmentation step.
- For each monotone missing dataset, using SAS PROC MI with MONOTONE REG model statement, the outcome variable at each post-baseline visit with missing values will be imputed sequentially with covariates constructed from their corresponding sets of preceding variables.

A 'complete' dataset with imputed values for the missing data is generated after the augmentation and imputation steps are completed.

Repetition of Imputations (K)

Repetition of imputations, K, must be determined in advance. When estimating the overall variance of multiple imputation, the additional sampling variance is the between-imputation variance divided by K. This value represents the sampling error associated with the overall or average coefficient estimates. It is used as a correction factor for using a specific number of imputations. The more imputations (K) are conducted, the more

precise the parameter estimates will be. For example, with a 1% power falloff tolerance in multiple imputation, as compared to an infinite number of imputations, multiple imputation requires 20 repetitions of imputation for 30% missing information and 40 repetitions for 50% missing information (Graham, Olchowski, and Gilreath 2007⁴). In the usual clinical settings expecting less than 30% missing information, K=30 repetitions are deemed sufficient. When missingness exceeds 30%, depending on the power falloff tolerance level, number of repetitions may need to be increased. Recent research⁴ suggested that the number of repetitions (K) should be at least equal to the percentage of missing (White et al., 2011⁶)

2.4 Derivation of Response Status and Non-Responder Imputation

Same as the abscess count, we also impute to obtain complete datasets for the inflammatory nodule count and the draining fistula count. For each 'complete' dataset, the imputed post-baseline values will be rounded to the same precision as the observed data. HiSCR status will be determined accordingly.

The imputed response status for missing due to reasons other than COVID-19 will be overridden by non-responder imputation (Section 2.1) to ensure that multiple imputation is only applied to missing due to COVID-19:

- Using NRI-C approach, all missing due to reasons other than COVID-19 will be categorized as non-responders, including visits after a subject receives any antibiotics for HS-related infections or discontinued study drug due to lack of efficacy. When determining the HiSCR response status, a subject with missing Baseline value will be counted as a non-responder at any post-baseline visit unless a subject's abscess, inflammatory nodule, and draining fistula counts are all zero at a specific visit, then the subject will be a HiSCR responder at that visit.
- The only exception is that a subject will be categorized as a responder for the visit if the subject is a responder both before and after an SAP-specified visit window in the particular Study Period.

2.5 Analysis

The statistical analysis will use the Cochran-Mantel-Haenszel (CMH) test adjusted by the actual stratification factors.

2.5.1 Analysis of Each Dataset

For each of the K 'complete' datasets, the CMH test will be used to estimate the treatment difference versus placebo and the corresponding standard error.

2.5.2 Synthesis of Results for Statistical Inference

The results from the K 'complete' datasets will be synthesized using the SAS procedure PROC MIANALYZE, following Rubin's formula (Rubin, 1987⁵), to derive the MI estimator of the treatment difference for the final inferences.

Rubin's formula

We fit the analysis model to the k^{th} 'complete' dataset, denoting the estimate of the treatment difference q by $\tilde{\theta}_k$ from the k^{th} 'complete' dataset, and denoting the corresponding estimate of the variance as V_k .

The MI estimator of q (point estimator obtained from PROC MIANALIZE), $\tilde{\theta}_{MI}$, is the average of the K individual estimators:

$$\tilde{\theta}_{MI} = \frac{1}{K} \sum_{k=1}^{K} \tilde{\theta}_{k}.$$

The estimated variance of $\tilde{\theta}_{MI}$, is a combination of the between- and within-imputation variability as follows:

$$V_{MI} = W + (1 + \frac{1}{\kappa})B,$$

where $W = \frac{1}{K} \sum_{k=1}^{K} V_k$ is the within-imputation variability and $B = \frac{1}{K-1} \sum_{k=1}^{K} (\tilde{\theta}_k - \tilde{\theta}_{MI})^2$ is the between-imputation variance.

It has been shown⁵ that the statistic

$$T = \frac{\tilde{\theta}_{MI} - \theta}{\sqrt{V_{MI}}}$$

has an approximate t_v distribution where $v = (K - 1)(1 + \frac{W}{B})^2$. Statistical inference, including hypothesis testing and confidence intervals for the treatment effect, will be based on this T-statistic.

3.0 Sample SAS Code

```
/*********
/*IMPUTATION ALGORITHM*/
/*********
/*NOTE: THIS APPROACH REQUIRES NO MISSING IN CATEGORICAL COVARIATES AND
REQUIRES AT LEAST ONE OBSERVATION IN BASELIBE OR ONE OF THE POST-
BASELINE VISIT*/
/*PRE-AUGMENTATION - CREATE DUMMY FOR CATEGORICAL VARIABLES*/
/***************
DATA COUNT 2; SET COUNT;
 /*THE MCMC STATMENT BELOW ASSUMES MULTI-VARIATE NORMAL*/
 /* USE ALL DATA IN THE IMPUTATION MODEL*/
 IF TRT01P="180mg" THEN TRT1=1; ELSE TRT1=0; /* CREATE DUMMY TREATMENT
VARIABLE FOR THE ANALYSIS STAGE*/
 IF TRT01P="360mg" THEN TRT2=1; ELSE TRT2=0; /* CREATE DUMMY TREATMENT
VARIABLE FOR THE ANALYSIS STAGE*/
 IF HURLEY=1 THEN HURLEY1 = 1 ELSE HURLEY1 = 0; /* CREATE DUMMY
VARIABLE FOR HURLEY STAGE 1*/
 IF HURLEY=2 THEN HURLEY2 = 1 ELSE HURLEY2 = 0; /* CREATE DUMMY
VARIABLE FOR HURLEY STAGE 2*/
/*AUGMENTATION STEP -- TO HAVE 30 MONOTONE MISSING DATASETS*/
PROC MI DATA= COUNT 2 OUT= COUNT MONO NIMPUTE=30 SEED= 21423 /*RANDOM
SEED PRE-DEFINED*/
 ROUND=. . . . . 1 1 1 1 1 1 1 /*VALUE ROUND TO INTEGER*/
 MIN=. . . . 0 0 0 0 0 0 0 0 /*MINIMUM VALUE OF COUNT IS 0*/
 MAX=. . . . . . . . . /*MAXIMUM VALUE*/
MCMC IMPUTE=MONOTONE ;
/*NOTE: CATEGORICAL VARIABLES SUCH AS TRT1 TRT2 HURLEY1 HURLEY2 ARE
DUMMY, CREATED ABOVE*/
/*NOTE: ALL OTHER NON-DUMMIED COVARIATES MUST BE CONTINUOUS*/
VAR TRT1 TRT2 TNFN HURLEY1 HURLEY2 BASE WK1 WK2 WK4 WK8 WK12 WK16;
/*CAUTION TO USE THE "BY" STATEMENT IN MCMC: */
```

```
/*MVN MODEL IS FITTED WITHIN EACH 'BY' GROUP, INSTEAD OF ACROSS ALL
GROUPS*/
RUN;
/*IMPUTATION STEP - DETERMINE IMPUTATION DISTRIBUTION AND RANDOMLY
IMPUTE MISSING VALUE TO GENERATE 'COMPLETE' DATASETS*/
/****************
PROC MI DATA= COUNT MONO OUT= COUNT FULL NIMPUTE=1 SEED= 21931 /*RANDOM
SEED PRE-DEFINED*/
 ROUND=. . . 1 1 1 1 1 1 1 /*VALUE ROUND TO INTEGER*/
 MIN=. . . 0 0 0 0 0 0 0 /*MINIMUM VALUE OF COUNT IS 0*/
 MAX=. . . . . . . . /*MAXIMUM VALUE*/
 MINMAXITER=1000;
 /*CLASS CATEGORICAL VARIABLES TRT1 AND REG2*/
 CLASS TRT01P TNFN HURLEY;
 VAR TRT01P TNFN HURLEY BASE WK1 WK2 WK4 WK8 WK12 WK16;
 MONOTONE REG (WK1 WK2 WK4 WK8 WK12 WK16); /* IMPUTED SEQUENTIALLY,
FROM WK 1 TO 16, WITH COVARIATES CONSTRUCTED FROM THE CORRESPONDING
PRECEDING VARIABLES*/
 BY IMPUTATION;
                                 /*FOR EACH OF THE 30 MONOTONE
MISSING DATASETS, IMPUTE A 'COMPLETE' DATASET*/
RUN;
/*We will get the imputed "complete" datasets for abscess, inflammatory
nodule, and draining fistula counts. For sample code below, we denote
the following variables: ABS16, INF16 and DRA16 as the corresponding
lesion count at Week 16; and AN16 as the sum of ABS16 and INF16.
Determine the HiSCR status at Week 16. */
DATA ALL; SET COUNT FULL;
   IF 0<= AN16 <=0.5*AN BASE AND ABS16<=ABS BASE AND DRA16 <= DRA BASE
THEN HISCR 16=1;
   ELSE HISCR 16=0;
RUN:
/***************************
/*
         DATA HANDLING STEPS TO MERGE COVID-19 STATUS OMITTED
*/
/*
            PLACE TO ADD DATA HANDLING AND MERGING STEPS
/***************************
/*FOR MI, SKIP THE FOLLOWING CODE, PROCEED TO THE CODE AFTER ANALYSIS
MODEL *//*OVERRIDE MISSING VALUES NOT DUE TO COVID-19 WITH TRADITIONAL
NRI*/
DATA ALLF; SET ALL;
```

```
/*COVID19 XX='Y' IF MISSING AT WEEK XX IS DUE TO COVID-19; IF NOT,
OVERRIDE WITH TRADITIONAL NRI*/
 /*VARIABLE HISCR NRI 16: TRADITIONAL NRI DATA AT WEEK 16, WHICH COVERS
THE SPECIAL HANDLING SUCH AS THE BEFORE-AND-AFTER EXCEPTION IN THE
PARTICULAR STUDY PERIOD*/
 IF COVID19 MISS NE 'Y' THEN HISCR 16 = HISCR NRI 16;
PROC SORT DATA=ALLF; BY IMPUTATION SUBJID; RUN;
/**********
/*ANALYSIS MODEL*/
/***********
/*KEY CODE: ANALYZING EACH 'COMPLETE' DATASET*/
/**********/
/*COMPARE TREATMENT PLACEBO AND 360mg ONLY*/
DATA ALL; SET ALL;
  WHERE TRT01P NE "180mg";
RUN;
/***********
/*INDIVIDUAL-LEVEL DATA --> # OF RESPONDERS & # OF SUBJECTS, TO BE READ-
IN TO PROC STDRATE */
PROC FREQ DATA=ALL;
 BY IMPUTATION;
 TABLES TRT2*STRATA*HISCR 16/LIST NOCUM NOPRINT OUT=COUNT TABLE;
 /*TRT2 = 1 as 360mg and 0 as placebo*/
DATA COUNT TABLE; SET COUNT TABLE;
 DROP PERCENT;
PROC TRANSPOSE DATA=COUNT TABLE OUT=FREQ TABLE PREFIX=RESP;
ID HISCR 16;
BY IMPUTATION TRT2 STRATA;
VAR COUNT;
RUN:
DATA FREQ TABLE1; SET FREQ TABLE;
 CASE=RESP1;
 SIZE=SUM(RESP0, RESP1);
 KEEP IMPUTATION TRT2 STRATA CASE SIZE;
RUN;
/*CALCULATE THE COMMON RISK DIFF FOR EACH COMPLETE DATASET*/
PROC STDRATE DATA=FREQ TABLE2
 METHOD=MH STAT=RISK EFFECT=DIFF;
 BY IMPUTATION;
 POPULATION GROUP=TRT2 EVENT=CASE TOTAL=SIZE;
 STRATA STRATA / ORDER=DATA STATS(CL=NONE) EFFECT;
 ODS OUTPUT EFFECT=EFFECT;
```

```
RUN;
/*COMBINING RESULTS USING PROC MIANALYZE*/
/*************************
PROC MIANALYZE DATA=EFFECT;
   ODS OUTPUT PARAMETERESTIMATES=RISK_DIFF_MH;
   MODELEFFECTS RiskDiff;
   STDERR StdErr;
RUN;
```

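### The sample code for the primary NRI-C analysis stores the non-responder override in dataset ALLF but analyses dataset ALL, in conflict with the SAP's own text

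*SAP*

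**What the plan says.** **The rule in words.** SAP 9.3.2 names NRI-C as the primary approach to missing data for HiSCR at Week 16. Under SAP 9.2.1 and Appendix E 2.1 and 2.4, data missing because of COVID-19 are multiply imputed. Data missing for any other reason count as non-response, unless the subject responds both before and after the visit window. Appendix E 2.4 says the override is there to confine imputation to COVID-19 gaps. Full MI is a sensitivity analysis only (9.3.3). Even there, 9.2.1 makes subjects with antibiotics for HS-related infections, or who stopped study drug for lack of efficacy, non-responders at later visits whatever was imputed.

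**The rule in code** (Appendix E 3.0; names given without underscores). A step creating ALLF from ALL applies "IF COVID19 MISS NE 'Y' THEN HISCR 16 = HISCR NRI 16". Next comes "PROC SORT DATA=ALLF; BY IMPUTATION SUBJID; RUN". The analysis model then opens with "DATA ALL; SET ALL", which drops the 180 mg arm, and counts responders with "PROC FREQ DATA=ALL". A comment above the override reads "FOR MI, SKIP THE FOLLOWING CODE, PROCEED TO THE CODE AFTER ANALYSIS". Further down, the listing creates a table in "DATA FREQ TABLE1; SET FREQ TABLE", but the risk-difference step is "PROC STDRATE DATA=FREQ TABLE2".

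**The concern.** This is the only code the SAP prints for its primary missing-data method, and its dataset names do not carry the primary rule through to the estimate. A programmer who completes the listing and keeps those names would impute every missing Week 16 value in the primary test. Subjects whom the text counts as non-responders could then enter as responders. These include subjects with HS antibiotics or lack-of-efficacy discontinuation, whose later visits Appendix E 2.1 sets to missing before imputation. Both ALL and ALLF exist and have the same structure, so the choice of ALL would produce no error message.

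**Working it through.** **1. Trace of the listing**

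| Step | Reads | Writes | Non-COVID override present? |
|---|---|---|---|
| Derive HiSCR from imputed counts | COUNT FULL | ALL | no |
| Placeholder for COVID-19 merge | – | – | – |
| Override | ALL | ALLF | yes |
| Sort | ALLF | ALLF | yes; last use of ALLF |
| Drop 180 mg | ALL | ALL | no |
| PROC FREQ, transpose, counts | ALL | COUNT TABLE, FREQ TABLE, FREQ TABLE1 | no |
| PROC STDRATE, then PROC MIANALYZE | FREQ TABLE2 | risk difference | no |

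The override never reaches the estimate. The placeholder comes before ALLF is created, so nothing placed there can redirect later steps that name ALL. The comment telling MI users to skip the override shows that ALLF was meant for NRI-C and ALL for MI. Missing underscores do not explain the mismatch, because ALL and ALLF are distinct names used consistently.

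**2. Planning figures used as inputs**

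SAP 2.4, Table 1: 74 per arm, placebo 26%, 360 mg 53%, difference 53 − 26 = 27 points, two-sided 0.025 per dose. The stated power for at least one dose (83.9%, 87.6%, 90.6%) is reproduced to within one point by simulating a continuity-corrected two-proportion test: 84.5%, 88.1%, 91.0%. The finding does not rest on these power figures.

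**3. Size of the effect**

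The missing shares m (non-COVID only) are assumptions. SAP 2.4 does not say whether its rates already count missing subjects as non-responders, so both readings are shown.

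*Reading A: the Table 1 rate p is the NRI rate.* The observed-case rate is p/(1 − m). If imputed subjects respond at that rate, ALL gives p + m·p/(1 − m) = p/(1 − m), while NRI-C stays at 27 points.

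- 15% missing on placebo, 5% on 360 mg: 0.53/0.95 − 0.26/0.85 = 0.558 − 0.306 = 25.2 points.
- 5% on placebo, 15% on 360 mg: 0.53/0.85 − 0.26/0.95 = 0.624 − 0.274 = 35.0 points.
- Equal 5%, 10%, 15%: 0.27/0.95, 0.27/0.90, 0.27/0.85 = 28.4, 30.0, 31.8 points.
- If imputed subjects respond at half the observed rate, the two unequal cases become 26.1 and 31.0 points.

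*Reading B: the Table 1 rate q is the rate when observed.* ALL stays at 27 points, and NRI-C gives q(1 − m) in each arm.

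| Missing, placebo / 360 mg | Correct NRI-C difference | Power, ALL / ALLF |
|---|---|---|
| 10% / 10% | 0.477 − 0.234 = 0.243 | 85% / 84% |
| 20% / 20% | 0.424 − 0.208 = 0.216 | 81% / 76% |
| 20% / 10% | 0.477 − 0.208 = 0.269 | 83% / 91% |
| 10% / 20% | 0.424 − 0.234 = 0.190 | 81% / 59% |

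The power column is a simulation of 360 mg against placebo: 1,500 trials per row, unstratified, 30 imputations, Rubin's rules, no COVID-19 missingness.

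The readings agree on direction in the 15%/5% cases. Under B, 15%/5% gives NRI-C 0.5035 − 0.2210 = 0.2825 against 0.27 from ALL, so ALL is lower. With the reverse it is 0.4505 − 0.2470 = 0.2035 against 0.27, so ALL is higher.

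**4. Two smaller gaps in the same lines**

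No printed step creates FREQ TABLE2. The denominator is built as "SIZE=SUM(RESP0, RESP1"), which tolerates an empty cell, but CASE is set directly to RESP1 and is therefore missing, not 0, in a stratum without responders. At a 26% rate the chance of such a placebo stratum is 0.74³ = 41% with 3 subjects, 0.74⁵ = 22% with 5 and 0.74¹⁰ = 5% with 10 (stratum sizes assumed). The fallback in SAP 9.1 covers strata without subjects, not strata without responders.

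**The case against.** The strongest reply is that this is demonstration code under unambiguous text. Appendix E 2.2 presents HiSCR as an example, the section is titled as sample code, and the comment beside the override states the intended rule. A programmer following the text would send NRI-C to ALLF. This stands, and it limits the finding to a conflict between text and code.

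The listing also cannot be run with one small repair. A reader might infer that correcting FREQ TABLE2 alone would let it run silently on the wrong data. The documents do not support that: the stratum variable, the Week 16 lesion variables, the conventional NRI variable and the merge of the three lesion types are also unprinted. Someone has to rebuild much of it, which makes unnoticed reuse less likely. It does not remove the error, because none of those missing pieces changes which dataset the analysis names.

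On the smaller points the reply is largely right. The marked placeholder acts on ALL before the MI branch, so it could hold the event override that 9.2.1 requires for MI. An unprinted step from FREQ TABLE1 to FREQ TABLE2 could also fill CASE with 0. The printed seeds, and the comment naming a variable REG2 that the listing lacks, change no result; the seed rule in 9.2.1 governs.

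Finally, the size rests on assumed missingness and on how Table 1 is read. That is correct, and it is why both readings are given.

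**Conclusion.** Wrong as written, in the sample code only. Once completed so that it runs, the Appendix E 3.0 listing would impute all missing data in the primary test, against 9.2.1 and Appendix E 2.1 and 2.4. The written NRI-C rule and the estimand are sound.

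The effect is nil without non-COVID missing data. Otherwise it depends on how much is missing and in which arm. Under the stated assumptions, a 27-point difference becomes about 25 or about 35 points on reading A. On reading B the code reports about 27 points where NRI-C would give about 19 to 27 (10–20% missing per arm).

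Three stronger conclusions are tempting but unsupported:

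- *The error favours the drug.* In the unequal 15%/5% illustrations, ALL lowers the difference when placebo has more missing data and raises it when 360 mg does.
- *The primary result would equal the planned MI sensitivity analysis.* The MI in 9.2.1 forces event subjects to non-response, and the printed ALL shows no such step.
- *The primary analysis itself is mis-specified or was run this way.* The text specifies it correctly, and the documents do not show the production code.

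**What to change.** In Appendix E 3.0:

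- For NRI-C, run the 180 mg exclusion and PROC FREQ on ALLF.
- For the MI sensitivity analysis, run them on ALL, after setting to non-responder every subject with HS antibiotics or lack-of-efficacy discontinuation before Week 16, as 9.2.1 requires. Print that step or state that it belongs in the placeholder.
- Make PROC STDRATE read the table that is created (FREQ TABLE1), and set CASE to 0 when RESP1 is missing, unless an unprinted step already does both.
- As housekeeping, mark the printed seeds as placeholders or replace them under the 9.2.1 rule, and remove the REG2 comment.

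The cost is a few lines of sample code before unblinding for the Primary Analysis. The NRI-C rule, the estimand, the data collected and the sample size do not change.
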